#### **3.2 Secondary Objectives and Endpoints**

2) To assess the real world clinical effectiveness of epoprostenol (Veletri®) therapy by collection of the following data (according to clinical practice), if available:

- demography
- vital signs
- exercise capacity as measured by six minute walking distance
- N-terminal pro-brain natriuretic peptide (NTproBNP)
- World Health Organization (WHO) functional class
- Borg dyspnea score
- blood gas analysis
- right heart size and function (presence/absence of pericardial effusion and tricuspid annular plane systolic excursion (TAPSE), right atrial and ventricular area, systolic pulmonary arterial pressure, right ventricular pump function, assessed by echocardiography)
- haemodynamics (right arterial pressure (RAP); mean pulmonary arterial pressure (mPAP); cardiac output (CO), cardiac index (CI); pulmonary vascular resistance (PVR); PVR index (PVRI); pulmonary capillary wedge pressure (PCWP) assessed by right heart catheterisation and tricuspid regurgitant jet velocity (TRJV) assessed by echocardiography)

- symptoms of PAH
- outcome (survival, transplant-free survival)

#### **4 Design of the Observational Trial**

This is a non-interventional, observational and prospective, multicenter study to evaluate the use, safety and tolerability of i.v. epoprostenol therapy (Veletri®) in routine practice according to the German Medicinal Products Act (AMG, §67(6)).

Patients with invasively diagnosed PAH receiving targeted PAH combination treatment in need of treatment escalation with i.v. epoprostenol, according to medically indicated decision on treatment-escalation, will be included in this non-interventional, observational study. This study is performed as a non-interventional trial using a prospective, open label, multicenter clinical study design with treatment according to current medical practice.

Patients will be assessed according to routine clinical examinations in their respective pulmonary hypertension expert center. According to the current guidelines, patients will be seen in the expert center about every three months. This will allow to collect data within the first 6 months of treatment and compare changes between baseline, 3 and 6 months (~24 weeks).

Routine medical examinations comprise of medical history, physical examination, electrocardiogram (ECG), laboratory testing (including NT-proBNP), echocardiography at rest, and right heart catheterization according to clinical practice of the PH center. If patients fulfill the inclusion criteria they will be invited to join the study. The prospective period of data collection will comprise of a ~24-week study period a follow-up phase of about 30±7 days.

Outcome (survival and transplant-free survival) of all patients will be assessed when the last patient has terminated his/her ~24 week observation period.

##### **4.1 Study population**

In this open label, multicenter non-interventional, observational study patients with PAH will receive medically indicated i.v. epoprostenol (Veletri®) according to a systematic drug management including initiation, administration, storage, handling of the infusion system and patient education. Patients in need of treatment escalation according to the current guidelines receiving at least dual oral combination treatment with two PAH-targeted drugs and having an unsatisfying long-term clinical response or are still in an intermediate or high risk group will be eligible for the study.

## 5 Trial Duration and Schedule

### 5.1 Study Phases

- Clinical visits and assessments will be scheduled according to the center's clinical practice about every 3 months.
- Treatment Duration: ~ 24 weeks

### 5.2 Trial Duration

The overall duration of the trial is expected to be approximately 3 ½ years. Recruitment of subjects will start in the fourth quarter of 2017. The actual overall duration or recruitment may vary.

Total trial duration:	[3 ½ years]
Beginning of the preparation Phase:	[Q4 2017]
FSI (First Subject In):	[Q1 2018]
LSI (Last Subject In):	[Q2 2020]
LSO (Last Subject Out):	[Q3 2020]
DBL (Data Base Lock):	[Q4 2020]
Statistical Analyses Completed:	[Q1 2021]
Trial Report Completed:	[Q1 2021]

## 6 Selection of Subjects

### 6.1 Number of Subjects

A sample of ~15 patients will be included into the observational study to gain insights into and collect data regarding the use, safety and tolerability of a systematic drug management of i.v. epoprostenol treatment (Veletri®).

### 6.2 General Criteria for Subjects' Selection

We will ascertain that only patients who are correctly diagnosed and are on PAH-targeted therapy will be included. Only patients on PAH targeted treatment in need of treatment escalation with i.v. epoprostenol will be included in this observational trial. Eligibility criteria are as follows:

### 6.3 Inclusion Criteria

1. male or female patients with pulmonary arterial hypertension (PAH)
2. adult patients having completed his/her 18th birthday

3. patients in need of treatment escalation with i.v. epoprostenol according to current guidelines
4. (PAH) confirmed by right heart catheter (RHC) before enrolment, i.e. mPAP  $\geq$ 25 mmHg at rest, PAWP  $\leq$ 15 mmHg
5. able to understand and willing to sign the Informed Consent Form.

#### **6.4 Exclusion Criteria**

1. known intolerance to epoprostenol or one of its excipients
2. participation in any clinical drug trial within 4 weeks prior to screening of this study and/or patient, who is scheduled to receive an investigational medicinal product (IMP) during the course of this non-interventional trial
3. pregnancy or lactation

#### **6.5 Criteria for Removal or Withdrawal**

##### **6.5.1 Withdrawal of Subjects**

Since the patients will be treated according to general practice and based on the medically indicated physician's decision (non-interventional trial), a patient will only be removed from this trial at his/her own request.

The reason for withdrawal must be recorded in the CRF and in the subject's medical records and the reason should be asked for as extensively as possible and documented. The patient will be informed that he/she is not obliged to give a reason for withdrawal.

## **7 Medicinal Product**

### **7.1 General Information about the Medicinal Product Under Observation (i.v. Epoprostenol)**

Medicinal product under observation: i.v. epoprostenol/Veletri®, solution

International Nonproprietary Name (INN): i.v. epoprostenol

ATC code: B01AC09

Route of administration: intravenous

Time and frequency of administration: continuous

Dosage: titration according to general practice and decision of the treating physician

Storage conditions: option to prepare and use your medicine immediately, or to prepare your medicine and store it in the refrigerator (36°F to 46°F/2°C to 8°C) for up to 8 days

Marketing authorization holder: Actelion Pharmaceuticals

## 7.2 Therapeutic Effects

Chronic pulmonary hypertension (PH) is associated with impaired exercise capacity, quality of life and right ventricular function.[1] The disease is characterized by an increase of pulmonary vascular resistance and pulmonary arterial pressure, leading to right heart insufficiency.[1, 2] Within the last decade, new disease-targeted medical therapies have been approved for treatment of pulmonary arterial hypertension (PAH).[3] Combinations of these agents have shown to further improve symptoms, 6-minute walking distance (6-MWD) and hemodynamics in PAH patients.[1, 3]

The loss of endogenous prostacyclin plays an important role in the pathogenesis of PAH. Prostacyclin has vasodilatory, anti-proliferative, anti-inflammatory and anti-thrombotic properties and is therefore an important target substance in PAH-specific therapy.[4] Epoprostenol was the first specific therapy approved for the treatment of PAH, after showing a positive effect on survival in otherwise treatment naïve patients.[5] Epoprostenol is chemically unstable with a short biological half-life of 3-5 minutes, and must be continuously administered by intravenous (i.v.) infusion using an external pump and in-dwelling central venous catheter.

The application of epoprostenol is therefore aggravated by its handling, which makes it a challenge for the patient to store and administer the medication.

Flolan® was the first epoprostenol drug that was made available for treatment of pulmonary arterial hypertension. Reconstituted flolan solution is stable at 2 - 8 °C for up to 48 hours. If used immediately, reconstituted flolan is stable for up to 12 hours at room temperature (< 25 °C), or prior to use at room temperature, reconstituted flolan may be stored at 2 - 8 °C for up to 40 hours. In this case, flolan should not be infused for over 8 hours at room temperature.

With Veletri® an improved epoprostenol solution has been therefore developed to facilitate storage and administration of the drug. It provides a better stability upon reconstitution is self-preserving, does not allow the growth of micro-organisms and allows reconstitution with readily available diluents.

## 7.3 Known Side Effects

Treatment with i.v. epoprostenol/Veletri® may cause side effects. The most common side effects seen in at least 1% of patients were:

- flushing
- headache
- nausea/vomiting
- low blood pressure

- anxiety/nervousness
- chest pain
- dizziness
- slow heartbeat
- abdominal pain
- pain in the muscles and/or ligaments and bones
- shortness of breath
- back pain
- sweating
- upset stomach
- numbness/increased sensitivity
- fast heartbeat

The most common side effects in patients with PAH due to unidentified or hereditary factors with at least 10% difference between the group that received epoprostenol and the group that received conventional therapy alone were:

- flu-like symptoms
- fast heartbeat
- flushing
- diarrhea
- nausea/vomiting
- jaw pain
- pain in the muscles and/or ligaments and bones
- anxiety/nervousness
- dizziness
- headache
- numbness/increased sensitivity/tingling

The most common side effects in patients with PAH due to connective tissue disease with at least 10% difference between the group that received epoprostenol and the group that received conventional therapy alone were:

- flushing
- low blood pressure
- lack of appetite
- nausea/vomiting
- diarrhea

- jaw pain
- neck/joint pain
- headache
- skin ulcer
- rash

#### **7.4 Dosage Schedule, Titration and Administration**

This non-interventional trial aims to investigate the use and titration of i.v. epoprostenol (Veletri®) in clinical practice. To guide physicians during the titration phase, the following informations will be provided, allowing a systematic approach to dosing. Informations given to the study phasicians include initiation, titration, dosage, known side effects and administration. This information is however not binding, but shall help the treating physician to handle i.v. administration of i.v. epoprostenol (Veletri®).

Official dosage recommendations are as follows:

- Initiation of chronic infusion of i.v. epoprostenol (Veletri®) at 2 ng/kg/min (or lower if not tolerated)
- Increase in increments of 2 ng/kg/min every 15 minutes or longer until a tolerance limit to the drug is established or further increases in the infusion rate are not clinically warranted.
- Decrease of dosage if dose-limiting pharmacologic effects occur
- In clinical trials, the most common dose-limiting adverse events were nausea, vomiting, hypotension, sepsis, headache, abdominal pain, or respiratory disorder (most treatment-limiting adverse events were not serious).

In the controlled 12-week trial in PAH/SSD, for example, the dose increased from a mean starting dose of 2.2 ng/kg/min. During the first 7 days of treatment, the dose was increased daily to a mean dose of 4.1 ng/kg/min on day 7 of treatment. At the end of week 12, the mean dose was 11.2 ng/kg/min. The mean incremental increase was 2 to 3 ng/kg/min every 3 weeks.

#### **Titration**

Adjust the infusion by 1- to 2-ng/kg/min increments at intervals sufficient to allow assessment of clinical response; these intervals should be at least 15 minutes.

In clinical trials, incremental increases in dose occurred at intervals of 24 to 48 hours or longer. Following establishment of new chronic infusion rate, observe the patient, and monitor standing

and supine blood pressure and heart rate for several hours to ensure that the new dose is tolerated.

During chronic infusion, the occurrence of dose-limiting pharmacological events may necessitate a decrease in infusion rate, but the adverse event may occasionally resolve without dosage adjustment. Make dosage decreases gradually in 2-ng/kg/min decrements every 15 minutes or longer until the dose-limiting effects resolve. Avoid abrupt withdrawal of i.v. epoprostenol (Veletri®) or sudden large reductions in infusion rates. Except in life-threatening situations (e.g., unconsciousness, collapse, etc.), infusion rates of i.v. epoprostenol (Veletri®) should be adjusted only under the direction of a physician.

### **Administration**

Veletri, once prepared as directed, is administered by continuous intravenous infusion via a central venous catheter using an ambulatory infusion pump. During initiation of treatment, i.v. epoprostenol (Veletri®) may be administered peripherally.

Infusion sets with an in-line 0.22 micron filter should be used.

## **8 Data Sources**

### **8.1 Variables**

Information will be collected as available and per clinical practice visit schedule. Data will be entered by the investigator / member of the study team into a standardized CRF.

Data will be collected for each patient at initiation of i.v. epoprostenol (Veletri®) and throughout the observational period from the existing medical record at any clinical visit on the respective CRF. If a patient's data collection is terminated, the date and reason for termination of data collection must be recorded on the CRF. Table 1 provides an overview of the variables collected at initiation of i.v. epoprostenol (Veletri®) and/or during the observation period (follow-up visits), if available, per clinical practice.

At initiation of a new i.v. epoprostenol (Veletri®) therapy, the data available at initiation of i.v. epoprostenol (Veletri®) will be collected for assessments stated above (points 8.1.1-8.1.10). Descriptions of clinical practice assessments are explicitly not used to alter or regulate clinical assessments in the participating centres.

According to the current guidelines, patients are likely to be seen in the expert center about every three months. This will allow to collect data within the first 6 months of treatment and compare changes between baseline, 3 and 6 months (~24 weeks).

### **8.1.1 Physical examination and demographic data**

The physical examination comprises measurement of body weight and height (height will be measured only once) and a routine internal medical examination. The results of these clinical physical examinations will be used to evaluate the inclusion and exclusion criteria and to document the health status before and following treatment with i.v. epoprostenol (Veletri®).

### **8.1.2 Hemodynamic parameters**

According to current guidelines the right heart catheterization (RHC) is being performed at the beginning and after six months of treatment with i.v. epoprostenol (Veletri®) [6, 7]. If performed at initiation of i.v. epoprostenol (Veletri®) therapy and after six months, right heart catheterisation (RHC) hemodynamic parameters will be collected [right atrial pressure, mean pulmonary arterial pressure (mPAP), pulmonary capillary wedge pressure (PAWP), cardiac output (CO), cardiac index (CI), and venous oxygen saturation (SvO2); heart rate, blood pressure.]

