## 10 Statistical Procedures

### 10.1 Sample Size Calculation

A sample of ~15 patients will be included into the observational study to gain insights into and collect data regarding the use, safety and tolerability of a systematic drug management of i.v. epoprostenol treatment (Veletri®).

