## **10.4 Statistical Methods**

### **10.4.1 General**

#### **Descriptive statistics**

All data (demographic and other baseline characteristics, continuous data at each routine visit and their change to baseline) will be listed and trial summary tables will be provided. Data of all centres will be pooled.

Descriptive statistics will be displayed, including the usual location and scale statistics (mean, median, standard deviation, standard error, first and third quartiles, minimum and maximum) and 95% confidence limits of mean and median.

Frequency tables for qualitative data will be provided.

If not mentioned otherwise, all statistical tests will be performed with a type I two-sided error rate of  $\alpha=0.05$

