#### **Primary endpoint**

The main parameters are safety and tolerability parameters of i.v. epoprostenol (Veletri®). Data regarding safety and tolerability will be collected by listings of adverse reactions during the course of the medically indicated treatment.

**Secondary efficacy variables** will be formally tested for statistical significance of a difference between baseline and 3 months; baseline and 6 months, respectively.

Secondary efficacy analysis comprises hemodynamics, echocardiography, lung function tests, 6MWD, Borg Dyspnea index, Modified Rodnan Skin Score, laboratory parameters, quality of life and safety parameters.

WHO functional class is supposed to either remain the same, improve by one or two categories, or deteriorate by one category in most cases. A change score (baseline minus end of study) will be calculated, which could go from -3 (class 4 at baseline and class 1 at end of study) to +1 (class 3 at baseline and class 4 at end of study). This will be analyzed using the Wilcoxon test.

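### The before-after tests have no place for patients who die or are not measured, so bias towards improvement is possible; separately, section 8.1.2 conflicts with section 8.1 and Table 1 on when catheter data are collected

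*Protocol*

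**What the plan says.** **Tests.** Section 10.4.1, under the primary endpoint subheading, states that the secondary efficacy variables "will be formally tested for statistical significance of a difference between baseline and 3 months; baseline and 6 months, respectively". The same section adds that "all statistical tests will be performed with a type I two-sided error rate of" 0.05. For WHO functional class it defines a change score between baseline and end of study, with a stated range of -3 to +1, and adds: "This will be analyzed using the Wilcoxon test".

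**Data.** Section 8.1 opens with "Information will be collected as available and per clinical practice visit schedule". Section 8.2 confirms that no assessment is added because of the study. Section 10.1 gives the size: "A sample of ~15 patients will be included into the observational study".

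**Catheter data.** Section 8.1.2 reads "If performed at initiation of i.v. epoprostenol (Veletri®) therapy and after six months, right heart catheterisation (RHC) hemodynamic parameters will be collected". Section 8.1 says that "the data available at initiation of i.v. epoprostenol (Veletri®) will be collected for assessments stated above (points 8.1.1-8.1.10"), a range that includes 8.1.2. Table 1 marks right heart catheterisation (RHC) once at initiation and again, in a separate column, at any follow-up visit. Inclusion criterion 4 in section 6.3 already requires the diagnosis to be confirmed by RHC before enrolment.

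**Deaths and transplants.** The safety analysis in section 10.4 summarises 6-month mortality and lists each death with its day and cause. Section 4 assesses survival and transplant-free survival in all patients at the end of the study. Section 6.5.1 removes a patient only at the patient's own request.

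**The concern.** A before-after difference needs two values. In a cohort escalated to intravenous treatment for severe disease, some patients may have no value at 3 or 6 months because they died or were too ill to be tested. If those patients would have shown the worst change, the tested group is selected for doing well, and a test can reach significance although the enrolled cohort did not improve. With about 15 patients, two or three such losses are enough to matter. These tests serve the secondary objective of real-world effectiveness.

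The RHC sentence raises a different problem, one of data capture. A site that takes it literally could leave the baseline haemodynamic page of the paper CRF blank for a patient who never reached a six-month catheterisation. Even the baseline table would then lean towards those who stayed in follow-up.

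**Working it through.** **No planned figure to reproduce.** The protocol gives no effect size, SD, death rate, transplant rate or dropout rate, and about 15 is stated without a calculation. What follows shows possible size under assumptions.

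**1. Shift in the mean among measured patients.**

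From the protocol: n = 15 and a two-sided level of 0.05. Assumed: true mean change 0, SD of change in 6-minute walking distance 80 m, 2 or 3 patients without a 6-month value, and correlation ρ between the variable that drives loss and the change itself.

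If the d patients lowest on that variable are lost, the expected mean in the rest is

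shift = ρ × SD × (sum of the d largest expected normal order statistics, n = 15) / (15 − d).

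The three largest are 1.736, 1.248 and 0.948.

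- d = 2: (1.736 + 1.248) / 13 = 0.230, and 0.230 × 80 = 18.4 m at ρ = 1, or 9.2 m at ρ = 0.5.
- d = 3: (1.736 + 1.248 + 0.948) / 12 = 0.328, and 0.328 × 80 = 26.2 m at ρ = 1, or 13.1 m at ρ = 0.5.
- ρ = 0: 0 m for any d.

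**2. False improvement.** This is the share of simulated cohorts in which a one-sample t-test on the remaining patients is significant in the favourable direction (nominal 2.5%).

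| Lost of 15 | ρ = 0 | ρ = 0.5 | ρ = 1 |
|---|---|---|---|
| 2 | 0 m, 2.5% | +9 m, about 6% | +18 m, about 17% |
| 3 | 0 m, 2.5% | +13 m, about 8% | +26 m, about 29% |

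The right-hand column assumes that loss picks out exactly the patients with the worst change, so it is an upper limit for that number lost.

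**3. How much the handling of a few deaths can decide.** Take 15 patients in whom every survivor improves, and use the exact two-sided Wilcoxon signed-rank test. With d deaths omitted, p = 2 / 2^(15−d). With deaths ranked worst, they take the largest ranks with a negative sign, so the negative rank sum is 15, 15 + 14 = 29, or 15 + 14 + 13 = 42.

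| Deaths | p, deaths omitted | p, deaths ranked worst |
|---|---|---|
| 1 | 0.0001 | 0.008 |
| 2 | 0.0002 | 0.083 |
| 3 | 0.0005 | 0.33 |

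Two deaths move the result across 0.05.

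**4. WHO class score.** The classes run from 1 to 4 and the stated score from -3 to +1. Every value presupposes a class at end of study, so a patient who has died has no score.

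**5. The RHC rules side by side.** Section 8.1.2 joins initiation and six months with 'and' inside one condition. Section 8.1 collects whatever is available at initiation, with no condition on a later catheterisation. Table 1 treats the two times separately. A patient with an RHC at initiation and none at six months contributes a baseline value under section 8.1 and Table 1, but not under a literal reading of 8.1.2.

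**The case against.** **The analysis set belongs to the SAP.** Nothing in the protocol restricts the tests to survivors or completers. Section 10.3 only repeats eligibility, and missing-data rules are commonly left to an SAP, which is not at hand here. This stands in part: silence on missing data is not itself a fault. But the protocol does fix paired comparisons, a WHO score without a value for death, and follow-up data limited to routine care. On those terms a patient without a follow-up value does not enter.

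**Deaths do not disappear.** A reader might infer that deaths and transplants vanish from the results. They do not: mortality is summarised, each death is listed, and survival and transplant-free survival are assessed for everyone. Nor does transplant end data collection, since removal is only at the patient's request. The loss is confined to the paired tests.

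**Overstatement is not shown.** A reader might also infer that improvement is overstated. The documents give no rates and no link between loss and change. Loss can run the other way, for instance when a stable patient is not catheterised again. This stands, and it is why the range starts at zero.

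**The RHC sentence may mean each time separately.** That is a fair reading, and section 8.1 and Table 1 support it. The documents therefore do not establish that baseline haemodynamics are kept only for patients with both catheterisations. What remains is a conflict in wording, which an SAP cannot repair because it does not govern what sites enter on the CRF.

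**Worst-rank analysis is severe.** With three deaths it gives p = 0.33 even when every survivor improves, and it answers a composite question about survival and function together. This is a good reason not to make it the main analysis.

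**Conclusion.** The point holds as a possible bias in secondary tests plus a conflict in a data-collection rule. Patients who die or are not measured by 3 or 6 months have no place in the before-after tests, and bias towards improvement can follow. With 15 patients, no true change, an SD of 80 m and 2 or 3 lost, the shift lies between 0 and +26 m and the false-improvement rate between 2.5% and about 29%. The SD, the number lost and the correlation are all assumptions. The primary objective, a description of use, safety and tolerability, is not affected. On RHC data, section 8.1.2 must be reconciled with section 8.1 and Table 1.

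**What to change.** 1. **Section 8.1.2.** Reword along these lines: *RHC values at initiation are collected for all patients where available; six-month values are collected if performed.* This agrees with section 8.1 and Table 1. It adds no procedure, since an RHC before enrolment is already an inclusion requirement. It should be settled before sites complete CRFs, because values not recorded must otherwise be retrieved later.

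2. **Section 10.4, tests.** Keep the change in measured patients. For 6-minute walking distance and WHO class, add a sensitivity analysis with the Wilcoxon signed-rank test in which death before the time point is ranked worst. State in advance whether transplant is ranked the same way. Fix the sign of the WHO score at the same time: baseline minus end of study for class 4 to class 1 is 4 − 1 = +3, whereas the text gives -3, and the worst rank needs an unambiguous direction.

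3. **Section 10.4, tables.** Beside each change, show the numbers enrolled, dead, transplanted, missing for other reasons, and analysed.

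The cost is some rewording and one extra analysis. That analysis is conservative, gives no mean change in metres, and may look less favourable than the result in measured patients.
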